### 3.2.2. Annualized Bleeding Rate

The number of bleeding episodes (BEs) during 12 months prior to the Screening visit will be collected in the Hemophilia History eCRF directly and will be used as the pre-screening rate. This form does not distinguish between treated or untreated bleeding episodes, only “total” pre-screening rate will be available.

The post-IP treated ABR will be calculated as:

$$[(\text{number of BEs requiring FVIII treatment recorded for the participant starting 3 weeks after IP infusion}) / (\text{number of days in observation period for the participant})] * 365.25.$$

If a FVIII prophylaxis regimen is initiated or resumed for a participant, then the time period (beginning with the first day of prophylaxis initiation or resumption) will be excluded from the treated ABR. The bleeding events after prophylaxis initiation or resumption will be excluded and the time period while on prophylaxis regimen will be deducted from the observation period, as well.

For all participants, treated bleeds (and days for the denominator) will be counted beginning on Day 22, and will stop counting when (the first of) any of the following happen:

1. The subject initiates or resumes routine prophylaxis (first day of resumption will not be counted);
2. The subject completes or discontinues (this day will be counted if data were collected);
3. Data cut or freeze date (this day will be counted if data were collected).

The number of days in the observation period will be calculated as (date of day before start of prophylactic dosing [or date of data cut or conclusion date] – [date of IP infusion + 21 days] + 1) which will then be annualized within the treated ABR formula. If no treated

bleeding episodes are reported during an observation period, treated ABR will be reported as zero.

During the post-IP period, multiple concurrent BEs (eg, two or more BEs that occur on the same date and time but in different sites in a participant) will be recorded as one bleed for overall treated ABR, but as separate BEs for that participant for treated ABR by location type (one episode for each unique location type, if they are different). Both spontaneous and traumatic treated bleeds will be counted towards the derivation of overall treated bleeding rate. BEs associated with a surgical procedure (perioperative and/or during the surgical rehabilitation period) will not be included in the treated ABR calculation.

Because only total ABR is available for pre-screening, overall total post-IP ABR will also be calculated, including BEs with and without FVIII treatment. A within-participant absolute difference, as well as percent reduction from pre-screening ABR, will be calculated for total ABR and summarized.

Treated and total ABRs will also be derived by location type (joint, target joint, soft tissue/muscle/other), by cause (spontaneous BE and traumatic BE), and by BE severity (mild, moderate, severe).

The five yearly windows defined in [Section 5.2](#) will be used for treated and total ABR analysis. An additional observation period is defined for the entire length of follow-up, >week 3 through Year 5.

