		
Section 3.2.2, ABR:
 
Added “Total” (treated+untreated) ABR calculation for post-study drug infusion.
 
Removed version of post-study drug infusion ABR which does NOT exclude any days after routine prophylaxis is resumed.
 
Sections 3.2.3 and 6.2.3, EQ-5D-5L:
 
Information on EQ-5D-5L Index score was added.
 
Sections 3.2.5 and 6.2.5, Vector Shedding:
 
For vector shedding analyses, removed ‘overall’ (across specimen types), and added the summary of time to peak value.
 
Section 3.5.1, Adverse Events:
 
Treatment-emergent adverse event (TEAE) definition changed to Pfizer’s standard that became effective May 2019: “An adverse event will now be considered a TEAE if the event started during the effective duration of treatment.”
 
Section 4, Analysis Sets:
 
The populations for analyses were revised. “Intent-To-Treat” population was removed since this population is the same as the Safety population (Safety is now considered primary). “Enrolled” analysis set was added. And “Per Protocol” was changed to “Evaluable” with modifications. Removed, “and have at least one post-baseline safety assessment” from the definition of the Safety population that is given in the protocol amendment 4. The Safety population will be all participants who received study intervention.
 
Section 5.3.1, COVID-19 Considerations: Added analyses to assess the impact of COVID-19.
 
Section 5.2.1.1:

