## 3.2. Secondary Endpoints

An e-Diary on a handheld device is to be provided to each participant at baseline, which is to be used until the end of study. The participants are required to enter any occurrence of bleeding episodes (including date, time, location, and etiology) and any exogenous FVIII replacement (including date, time, reason, and dose) required to treat the bleeds in the e-Diary throughout follow-up regardless of whether or not the participant has initiated or resumed prophylactic therapy. If a participant has to initiate or resume FVIII prophylaxis

treatment, prophylaxis FVIII infusion data will not have to be reported on the e-Diary after Month 24 but the prescribed FVIII replacement regimen will be recorded in the eCRF by the sites and used to derive infusion data. On-demand and preventative infusions will continue to be required to be reported on the e-Diary throughout follow-up.

The protocol recommends prophylaxis FVIII treatment for up to approximately 2 weeks post PF-07055480 infusion (and may be used longer than 2 weeks, per investigator discretion), to provide protection against bleeding while allowing sufficient time for PF-07055480 to start FVIII expression. Participants are then switched to on-demand regimen. The first 3 weeks following treatment with PF-07055480 will not be considered in the analysis of annualized infusion rate (AIR) and annualized bleeding rate (ABR), to exclude contributions from prior routine prophylaxis, which could have been continued during this period.

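### ABR counting starts at Day 22 for everyone and removes only prophylaxis that is initiated or resumed, so a prior regimen still running at Day 22 is counted

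*SAP*

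**What the plan says.** SAP 3.2 gives the reason for leaving out the first 3 weeks: "to exclude contributions from prior routine prophylaxis, which could have been continued during this period". The same paragraph says that post-infusion prophylaxis is recommended for up to about 2 weeks "and may be used longer than 2 weeks, per investigator discretion". No upper limit is given. Protocol 6.5 requires participants on prior prophylaxis to switch to on-demand treatment at about 2 weeks, on condition that the data show this to be safe.

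SAP 3.2.2 sets the counting rule: "For all participants, treated bleeds (and days for the denominator) will be counted beginning on Day 22, and will stop counting when" the first of three events occurs. These are initiation or resumption of routine prophylaxis, completion or discontinuation, and data cut or freeze. The paragraph on exclusion opens with the same trigger, a regimen that is initiated or resumed, and continues: "The bleeding events after prophylaxis initiation or resumption will be excluded and the time period while on prophylaxis regimen will be deducted". In the day-count formula, the end date for a participant who goes on prophylaxis is the "date of day before start of prophylactic dosing". If no treated "bleeding episodes are reported during an observation period, treated ABR will be reported as zero".

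Total ABR is introduced with the words "overall total post-IP ABR will also be calculated, including BEs with and without FVIII treatment". SAP 6.2.2 includes all participants whatever their prior prophylaxis status.

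**The concern.** The 3-week exclusion has a stated purpose, and the counting rule secures it only if every participant has stopped prior prophylaxis by Day 21. The plan allows for participants who have not. For such a participant, ABR mixes protected days into what is meant to be the bleeding rate without prior prophylaxis. If he bleeds less while protected, his post-infusion ABR comes out too low, which favours the product. Total ABR carries the comparison with the pre-screening rate, so the reported percent reduction would be affected in the same direction. With about 20 participants spread over four cohorts, one affected participant can be visible in a dose-level summary.

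**Working it through.** **1. Does any sentence cover a regimen that never stopped?**

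- Stop list: the trigger is initiating or resuming. Continuing is not listed.
- Deduction of time while on prophylaxis: this sentence belongs to the paragraph conditioned on initiation or resumption, and it refers to bleeds after that event. It does not reach an unbroken prior regimen.
- Day-count formula: suppose the start of prophylactic dosing meant the start of the prior regimen. The period is (start − 1) − (infusion + 21) + 1. A start on the infusion date gives −1 − 21 + 1 = −21 days; a start 60 days earlier gives −81. That reading cannot be intended.

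So carried-over prophylaxis is counted from Day 22.

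**2. Inputs for the size**

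- Relative day 1 is the infusion date (SAP 5), so infusion + 21 days is Day 22. The formula and the text agree.
- The Year 1 window is Day 22 to Day 365 (SAP 5.2.1.1): 365 − 22 + 1 = 344 days.
- Five years, taken as Day 1826: 1826 − 22 + 1 = 1805 days.
- Assumed: the last day of carry-over, D, and f, the protected bleed rate divided by the unprotected rate. The documents give neither.

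**3. Formula**

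Protected days counted: p = D − 21. For an unprotected rate r and a window of N days, the ABR as written is r × [(N − p) + f × p] / N = r × [1 − (p/N)(1 − f)]. The proportional understatement is (p/N)(1 − f).

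**4. Results**

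| D (assumed) | p | Year 1, f = 0 | Year 1, f = 0.5 | 5 years, f = 0 |
|---|---|---|---|---|
| 21 | 0 | 0 | 0 | 0 |
| 28 | 7 | 7/344 = 2.0% | 1.0% | 7/1805 = 0.4% |
| 56 | 35 | 35/344 = 10.2% | 5.1% | 1.9% |
| 84 | 63 | 63/344 = 18.3% | 9.2% | 3.5% |

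As an example, take 12 bleeds per year unprotected. This is the on-demand entry threshold in Protocol 5.1; using it after infusion is an assumption. With f = 0, the Year 1 ABR as written is 12 × 337/344 = 11.8 for D = 28 and 12 × 281/344 = 9.8 for D = 84, against 12.0 once the protected days are excluded.

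**The case against.** The best defence is that 3 weeks is itself the allowance for overrun. The switch is planned at about 2 weeks (Protocol 6.1.1 and 6.5), so Day 22 leaves roughly a week of margin, and a fixed start is a common, simple convention. Participants treated on demand before the study cannot be affected. Carry-over would also show up: post-infusion FVIII therapy, bleeds and annualized rates are listed by participant, and the annualized infusion rate counts infusions for any purpose from Day 22. All of this stands. It means that the affected group may be empty and that Day 28 is closer to the planned switch than Day 56 or Day 84. It does not supply a rule for a participant who is still on his prior regimen, whom the plan expressly allows for.

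A reader might infer two larger faults.

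- **Later prophylaxis that ends.** Taken alone, the deduction sentence drops all later bleeds but removes only the days on the regimen, so later off-prophylaxis days would stay in the denominator without their bleeds. The documents do not support computing ABR that way. The excluded period begins with the first day of prophylaxis, counting stops at the first listed event, and the formula ends the day before prophylaxis starts. The phrase is loose, but the formula settles the calculation.
- **No prophylaxis exclusion for total ABR.** SAP 3.2.2 states the exclusion for treated ABR only. However, it gives both rates the same windows, and SAP 6.2.2 lists ABR after initiation or resumption separately for both. The version history records an earlier step, "Removed version of post-study drug infusion ABR which does NOT exclude any days after routine prophylaxis is resumed", which is evidence of intent only. The same period is largely implied and only needs stating.

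**Conclusion.** The gap is real and limited. As written, SAP 3.2.2 counts an uninterrupted prior prophylaxis regimen from Day 22 onward, contrary to the purpose given in SAP 3.2. The size depends on how many participants carry over and for how long, which the documents do not give. The understatement of at most about 2% for carry-over to Day 28 applies to one participant's Year 1 rate; the larger figures rest on assumed dates. The direction is downward only if bleeding is lower while protected. ABR is a secondary endpoint in a purely descriptive analysis (SAP 5.1), so no error rate or decision rule is affected. It should still be corrected, because a stated rule gives the wrong rate for a case that the plan permits. The points on the deduction phrase, total ABR, the no-bleed percentage and empty windows are clarifications of wording and add nothing to the size.

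**What to change.** Analysis definition only; when prophylaxis should stop is not at issue.

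1. Start each participant's ABR count, for bleeds and days alike, at the later of Day 22 and the day after carried-over routine prophylaxis ends. Take the end date from the recorded FVIII administration dates and reasons.
2. Amend the phrase on deducting time while on the regimen so that it matches the permanent censoring already in the stop list and day formula.
3. State that the same period governs total ABR and the percentage of participants with no bleeds in SAP 6.2.2.
4. Where a window has no countable days, report ABR as not evaluable instead of zero. This would also cover a participant who stays on prior prophylaxis throughout a window.

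The cost is a few SAP sentences and modest programming. The e-Diary already records the date, time and reason of FVIII infusions. Only for a regimen running past Month 24, when prophylaxis infusions need no longer be entered there, would the eCRF regimen record be needed. The downside is slightly less at-risk time for affected participants: 7 to 63 fewer days in Year 1 in the examples above.

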##### 5.2.1.1. Yearly Windowing

The following windowing option may be used when each yearly observation period used for analysis will be 365 days. Any dates beyond 1460 days will also be included with Year 5 for analysis. Post-infusion AIR and ABR yearly windowing begins with 3 weeks after the IP infusion where day is calculated relative to the IP infusion date. Post-infusion AE yearly windowing begins on the IP infusion date.

Window name	Derivation
Year 1	Day 22 $\leq$ Year 1 $\leq$ Day 365
Year 2	Day 365 < Year 2 $\leq$ Day 730
Year 3	Day 730 < Year 3 $\leq$ Day 1095
Year 4	Day 1095 < Year 4 $\leq$ Day 1460
Year 5	Day 1460 < Year 5

Further details of windowing will be described separately for each endpoint in [Section 2.1](#), as applicable.

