### **5.2.3. Analyses for Continuous Endpoints**

Summary descriptive statistics for continuous variables will include the number of observations with non-missing values, mean, standard deviation, median, first quartile, third quartile, minimum, and maximum values.

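### Treated ABR is annualised over whatever days precede prophylaxis and averaged with equal weight, so one short window can dominate a dose level's yearly mean, SD and maximum

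*SAP*

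**What the plan says.** SAP 3.2.2 defines a participant's treated ABR as treated bleeds divided by the "number of days in observation period for the participant", times 365.25. Three points in that section fix the window:

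- The counting rule is that "treated bleeds (and days for the denominator) will be counted beginning on Day 22, and will stop counting when (the first of" three listed events) occurs. The event that heads the list is the start of prophylaxis: "The subject initiates or resumes routine prophylaxis (first day of resumption will not be counted").
- What follows is removed from both parts of the ratio: "The bleeding events after prophylaxis initiation or resumption will be excluded and the time period while on prophylaxis regimen will be deducted".
- If no treated "bleeding episodes are reported during an observation period, treated ABR will be reported as zero". No minimum number of days is attached to this rule or to the rate itself.

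The yearly windows "will be used for treated and total ABR analysis", and a further period covers all follow-up after week 3. SAP 5.2.1.1 describes the option in which "each yearly observation period used for analysis will be 365 days"; Year 1 for ABR runs from Day 22 to Day 365, and Year 2 starts after Day 365.

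SAP 6.2.2 summarises the rates by dose level and time interval in the Safety population. SAP 5.2.3 supplies the statistics: "Summary descriptive statistics for continuous variables will include the number of observations with non-missing values, mean, standard deviation, median", then quartiles, minimum and maximum. Neither section plans total bleeds over total time, a weighting by observed time, or observation days beside the rate.

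**The concern.** Ending treated ABR at prophylaxis is reasonable in itself. The difficulty is what is done with the shortened window. A bleed count over a few days, multiplied up to a year, is a very unstable number, yet it enters the dose-level mean with the same weight as a full year's observation. Equal weighting is not stated in words; it follows from applying plain descriptive statistics to one value per participant.

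If the decision to start prophylaxis tends to follow a bleed, the window's length depends on the outcome. Short windows then tend to end in a bleed, and the average of the ratios is pushed upward. Protocol 6.1.1 and 6.5 say that participants adjust FVIII use according to need, which makes such a link plausible but does not establish it.

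Bleeding frequency is a secondary endpoint, and in a descriptive study the summary table is the result. About 20 participants are spread over the four cohorts in SAP 6.5.3, and SAP 2 has the committee decide on escalation after two participants, so one value can carry a whole row.

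**Working it through.** **Inputs from the documents.** Rate = bleeds / days × 365.25, counting from Day 22 and stopping the day before prophylaxis (SAP 3.2.2). Day 1 is the infusion date (SAP 5). Year 1 has 365 − 22 + 1 = 344 days; Year 2 has 730 − 365 = 365 days (SAP 5.2.1.1). The plan states no ABR figure to reproduce.

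**Assumed inputs.** Participants per dose level, days observed before prophylaxis, and bleeds in the other participants. The documents give none of these, so ranges are shown.

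**Worked case, Year 2, n = 5.** One participant bleeds once and starts prophylaxis on Day 373. His Year 2 window is Days 366 to 372, which is 7 days. The other four have no bleeds in 365 days.

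- His ABR: 1 / 7 × 365.25 = 52.18.
- Cohort mean: 52.18 / 5 = 10.44.
- SD: √[((52.18 − 10.44)² + 4 × 10.44²) / 4] = 23.3.
- Median, Q1 and Q3: 0. Maximum: 52.18.
- Pooled rate: 1 / (4 × 365 + 7) × 365.25 = 0.25.

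**Range over days observed** (one bleed in d days; the others bleed-free for 365 days):

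| d | Participant ABR | n = 5: mean / median / pooled | n = 2: mean = median / pooled |
|---|---|---|---|
| 3 | 121.75 | 24.35 / 0 / 0.25 | 60.88 / 0.99 |
| 7 | 52.18 | 10.44 / 0 / 0.25 | 26.09 / 0.98 |
| 14 | 26.09 | 5.22 / 0 / 0.25 | 13.04 / 0.96 |
| 30 | 12.18 | 2.44 / 0 / 0.25 | 6.09 / 0.92 |
| 90 | 4.06 | 0.81 / 0 / 0.24 | 2.03 / 0.80 |

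If the other four participants each have one bleed in the year, the 7-day participant supplies 93% of the n = 5 mean (11.24, against a pooled 1.24). At n = 9 he supplies 87% (6.69 against 1.12).

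**Whole follow-up, same participant.** His observed time is 344 + 7 = 351 days, so his ABR is 1 / 351 × 365.25 = 1.04. With the other four bleed-free throughout, the cohort mean is 1.04 / 5 = 0.21.

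**Average effect if bleeds trigger prophylaxis.** Assume a constant true rate of 2 per year and a 365-day window. If prophylaxis always starts the day after the first bleed, the expected participant ABR is 10.35, while expected bleeds over expected time is 1.99. In simulated cohorts of five with prophylaxis the day after only some bleeds, the planned mean averages about 4.4 to 4.7 when 25% of bleeds trigger it and 6.6 to 6.9 when 50% do. The pooled rate averages about 2.1 and 2.2. With a 7-day delay the planned mean falls to about 3.2 to 3.4 and 4.2 to 4.3.

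**The pooled rate when participants differ.** Those runs give every participant the same rate, which favours pooling. With gamma-distributed individual rates (assumed mean 2, shape 1 or 0.5) and next-day prophylaxis after 25% or 50% of bleeds, the pooled rate averages about 1.3 to 1.75, below the true mean of 2. Frequent bleeders leave early and contribute little time.

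**The case against.** The strongest reply is that the plan already holds several safeguards, and much of it stands.

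- The median and quartiles are planned. In the worked case the row would show a median of 0 beside a maximum of 52.2, so the outlier would be visible. In a cohort of two, though, the median equals the mean.
- The whole-follow-up period and the count of participants with no bleeds (4 of 5 here) are planned and far less sensitive. A participant starting prophylaxis soon after Day 22 would still have a short whole-follow-up window.
- SAP 6.5.2 lists each participant's duration in each year, and SAP 6.2.2 lists the bleeds and rates. The duration listed is time in the study; it is not said to exclude time on prophylaxis, and it does not sit beside the rate.
- The analysis is descriptive (SAP 5.1), so no test or error rate is affected. Under Protocol 4.1 the dose decisions rest on safety and FVIII levels, not on ABR.
- A short bleed-free window counts as 0 with full weight, so the distortion can also run downward.

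A reader might go further and infer that the pooled rate should become the headline, with participant ABRs moved to a listing. The documents do not support that. SAP 3.3.5 itself notes high variability of transgene expression between participants, and in that setting the pooled rate gives less weight to early failures and can understate bleeding. In the worked case, 0.25 alone would hide the one participant who needed prophylaxis.

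**Conclusion.** The point holds for the yearly treated-ABR mean, SD and maximum by dose level, and for the median where a cohort has two participants. Followed exactly, the plan can report a mean of 10.4 where one bleed occurred in 1,467 participant-days (4 × 365 + 7). The upward direction rests on a bleed prompting prophylaxis, which the documents do not state. The size rests on assumed prophylaxis dates, bleeding rates and cohort sizes, so the figures are illustrations and not predictions.

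Two further inferences should be resisted. One is that the year-to-year ABR trend as a whole reflects prophylaxis timing and not bleeding; the medians, the whole-follow-up summary and the bleed-free percentages argue against that. The other is that the comparison with the pre-screening rate is distorted in the same way. That comparison uses total ABR, whereas the stop rule is written for treated bleeds, and SAP 3.2.2 does not say whether total ABR is cut likewise. That is a gap to close, not a demonstrated error.

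The change is worth making because it is cheap and prevents a misleading table entry.

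**What to change.** In SAP 6.2.2, for each dose level and each window, keep the participant-level statistics and add beside them:

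- total treated bleeds;
- total observed participant-days;
- the pooled rate, total treated bleeds / total participant-days × 365.25.

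In the ABR listing, show each participant's ABR observation days per window, after time on prophylaxis is removed, and flag windows shorter than a threshold fixed in advance. The table of days observed above shows how fast a single bleed inflates the rate as the window shortens and can inform that choice.

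Add a note that the pooled rate gives less weight to participants who start prophylaxis early, so it can understate the average participant's rate when rates differ between participants.

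In SAP 3.2.2, state whether total ABR is cut at prophylaxis in the same way as treated ABR.

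The cost is SAP wording, one or two extra table rows and an extra listing column, all from data already collected. Data collection and participant care do not change.

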### 6.2.2. Annualized Bleeding Rate

Both pre-screening and post-IP infusion total ABRs will be summarized together with the difference and percent reduction, along with the summary of post-IP infusion treated ABR, for the Safety population by dose level. The number and percentage of participants with no bleeds post-IP infusion will also be summarized by dose level. All participants, regardless of prior prophylaxis treatment status, will be included. Post-IP infusion treated and total ABR will be summarized by the time intervals as specified in [Section 3.2.2](#).

Separate summaries of treated and total post-IP infusion ABR by location type (joint, target joint, soft tissue/muscle/other), by cause (spontaneous and traumatic BEs), and by BE severity will be created for the Safety population stratifying by dose level.

Additional analyses may be performed using an Evaluable population, if appropriate.

Listings of BEs recorded during the study and the annualized rates will be created. The listing will additionally include treated and total post-initiation or post-resumption of prophylaxis ABR for the participants who initiated or resumed a FVIII prophylaxis treatment during the post-infusion period.

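### The treated ABR drops the whole first calendar day of prophylaxis, so a treated bleed earlier that day, including one that prompts the resumption, is excluded although it occurred off prophylaxis

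*SAP*

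**What the plan says.** SAP 3.2.2 defines treated ABR as treated bleeds divided by days in the observation period, times 365.25. It removes the first day of prophylaxis in three places:

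- The time on prophylaxis, "beginning with the first day of prophylaxis initiation or resumption) will be excluded from the treated ABR".
- For every participant, "treated bleeds (and days for the denominator) will be counted beginning on Day 22", and counting ends at the first of three events. The first is "The subject initiates or resumes routine prophylaxis (first day of resumption will not be counted"). The other two, study completion or discontinuation and the data cut, do count their own day if data were collected.
- The denominator runs to the "date of day before start of prophylactic dosing".

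One sentence is looser: "The bleeding events after prophylaxis initiation or resumption will be excluded". If no treated "bleeding episodes are reported during an observation period, treated ABR will be reported as zero".

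On timing data, SAP 3.2 has participants enter in the e-Diary "any occurrence of bleeding episodes (including date, time, location, and etiology"). Protocol 6.5 asks them to record the date and time of each FVIII administration. However, Protocol 8.1.3 and SAP 3.2 say that after Month 24 prophylaxis infusions need not be entered in the e-Diary. SAP 3.2 then derives infusion data from the prescribed regimen in the eCRF.

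**The concern.** Treated ABR is meant to describe bleeding while the participant relies on the gene therapy and not on prophylaxis. A treated bleed at 08:00 followed by a first prophylactic dose at 14:00 belongs to that period. The rule discards it because it works in whole calendar days.

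Losing one day of denominator is trivial, but losing one bleed is not. Nor is the loss neutral. Of the three stopping events, prophylaxis is the one a bleed can readily prompt, and it is the only one whose own day is dropped. A bleed that leads to same-day resumption therefore removes itself from the count, in a participant for whom expression may have become inadequate.

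The wording is also inconsistent. A bleed earlier on the start date is not *after* initiation, so the looser sentence would keep it, while the stop rule and the denominator formula discard its day. Two programmers following the same section could report different values for the same participant.

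**Working it through.** The documents state no figure to reproduce here, so the check applies the SAP formula.

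**Inputs.** Relative Day 1 is the infusion date (SAP 5), so Day 22 is infusion date + 21. Let P be the relative day of the first prophylactic dose.

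**Day count.** Days = (P - 1) - 22 + 1 = P - 22, that is, Days 22 to P - 1. The formula and the stop rule agree: day P is out of both numerator and denominator.

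**Direction.** With k treated bleeds in D days before P and one more on day P, the SAP gives k/D, and counting that day gives (k+1)/(D+1). The second is larger whenever D > k, which holds unless there is at least one bleed per day. The exclusion of such a bleed therefore lowers treated ABR.

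**One treated bleed, on day P, none earlier:**

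| First prophylaxis day P | SAP as written | Day P counted |
|---|---|---|
| 112 | 0/90 = 0 | 1/91 x 365.25 = 4.01 |
| 204 | 0/182 = 0 | 1/183 x 365.25 = 2.00 |
| 387 | 0/365 = 0 | 1/366 x 365.25 = 1.00 |
| 400 | 0/378 = 0 | 1/379 x 365.25 = 0.96 |
| 752 | 0/730 = 0 | 1/731 x 365.25 = 0.50 |

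At P = 387, the same bleed one day earlier gives 1/365 x 365.25 = 1.00 under the SAP. A one-day difference in start date decides between 0 and 1.

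**Earlier bleeds.** At P = 387 with 1 or 2 earlier treated bleeds, the SAP gives 1.00 or 2.00, against 2.00 or 2.99. The last bleed is still lost, but the value is not zero.

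**Yearly windows (SAP 5.2.1.1).** Year 2 begins on Day 366. With P = 400, the SAP gives 0 over 34 days (Days 366 to 399). Counting Day 400 gives 1/35 x 365.25 = 10.4.

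**Effect on a dose-level mean.** One such participant at P = 387 shifts the mean by 1.00/n: 0.50, 0.20, 0.10 or 0.05 for assumed n = 2, 5, 10 or 20.

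**Illustrative simulation.** Assumptions: constant rate of 2 treated bleeds a year, Days 22 to 365, and a share p of bleeds that each prompt prophylaxis the same day. The documents give no value for p.

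| p | Summary | As written | Trigger bleed counted |
|---|---|---|---|
| 25% | Pooled (total bleeds / total days) | 1.5 | 2.0 |
| 25% | Median of individual ABRs | 1.06 | 2.12 |
| 25% | Mean of individual ABRs | 1.5 | about 4.5 |
| 50% | Pooled | 1.0 | 2.0 |
| 50% | Median | 0 | 2.24 |
| 50% | Mean | 1.0 | about 6.5 |

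As written, the pooled rate is 2 x (1 - p). Counting the trigger bleed restores the true pooled rate of 2 and brings the median close to it. The mean of individual ABRs overshoots, because a short interval that ends in a bleed annualises to a very large value.

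**The case against.** Several points on the other side stand.

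- **The trigger is narrow.** The bleed and the start of a routine regimen must share a calendar date. A bleed treated on demand, with prophylaxis from the next day, is counted in full. The documents give no frequency for same-day starts.
- **Resumption is not hidden.** AIR includes prophylaxis infusions (SAP 3.2.1), bleeding episodes are listed, and ABR after resumption is listed (SAP 6.2.2). None of these corrects the treated-ABR summary, but a careful reader could find the case.
- **Counting the bleed is not free of bias.** SAP 5.2.3 summarises continuous variables by mean and median, among other statistics, and the mean of individual ABRs moves from too low to too high.

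A reader might also infer three stronger things that the documents do not support.

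- **That the percentage without bleeds is overstated**, for instance 100% instead of 80% in a cohort of five. SAP 6.2.2 says "The number and percentage of participants with no bleeds post-IP infusion will also be summarized by dose level". It does not say treated bleeds, and it does not say the prophylaxis stop rule applies.
- **That the post-resumption listing will show the bleed as one on prophylaxis.** SAP 6.2.2 does not say whether that listing includes the first day.
- **That e-Diary times always settle the order.** For resumption after Month 24, which covers three of the five follow-up years, the documents promise no e-Diary time for the first prophylactic dose.

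**Conclusion.** The point holds. SAP 3.2.2 excludes a treated bleed that begins off prophylaxis if prophylaxis starts later the same day, and the section's own wording conflicts on whether it should. The exclusion lowers treated ABR. It gives zero when no other treated bleed is counted in the window, and it matters most in yearly windows with little time before resumption. For one participant with a single such bleed, the difference ranges from 0.50 (start on Day 752) to 4.01 (start on Day 112) over the whole follow-up, and is 10.4 in Year 2 for a start on Day 400.

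The effect on the study as a whole cannot be stated, because it depends on how many bleeds prompt a same-day start; the simulated shares are assumptions. With about 20 participants in four dose cohorts, one case can visibly move a cohort summary. The endpoint is secondary and the analysis purely descriptive (SAP 5.1), so no error rate or sample size is affected. A reader might infer that the rule invalidates the bleeding results or conceals loss of effect. That goes too far, given the AIR, the listings and the unknown frequency. This should be fixed, but it is not critical.

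**What to change.** In SAP 3.2.2:

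1. Count every treated bleed with onset before the first prophylactic infusion, including on the same date, and include that day in the denominator. Reword the stop rule, the excluded period, the denominator end date and the sentence on bleeds after resumption so that all four agree.
2. Use e-Diary times where they exist. Where the time of the first dose is missing, which is likely after Month 24, count the bleed as pre-prophylaxis and flag it in the listing. This fallback may include some bleeds that followed the first dose, so the flag is needed.
3. Report the pooled rate (total treated bleeds / total days x 365.25) by dose level alongside the median.
4. State whether the same split applies to total ABR, to the percentage with no bleeds and to the post-resumption ABR listing in SAP 6.2.2.

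The cost is a few sentences, a small programming change and one added summary line, with no new data collection. The downside is that treated ABR becomes less favourable and the mean of individual ABRs can be unstable when prophylaxis resumes early. In the extreme, a bleed with resumption on Day 22 has a zero-day denominator now and would give 1/1 x 365.25 = 365.25 after the change. The pooled rate and median should therefore carry the interpretation.
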